Endpoint	Primary Endpoint: Opioid utilization for the first 72 hours after surgery, including during surgery, calculated as morphine equivalent. Secondary Endpoints: Opioid consumption Post-operatively Patient reported VAS scores in PACU Length of stay in PACU Patient reported VAS scores on POD 1, POD 2, POD 3, POD 7 Reaction to IPACK block Incidence of postoperative complications
Study Duration	The study will continue until 50 subjects are enrolled per arm, to allow for potential dropout and increased power.
Participant Duration	Each participant will be enrolled on DOS and complete their final follow up on postoperative day seven.
Duration of IP administration	Once during surgery
Population	50 patients per study arm scheduled for ACLR with BPTB autograft
Study Sites	NYU Langone Orthopedic Hospital and NYU Ambulatory Surgery Center at 38 th street
Number of participants	100
Description of Study Agent/Procedure	Patients in both the study and control group will receive the standard of care adductor canal block composed of 15 mL of Bupivacaine (0.25%). Patients in the study group will receive the additional IPACK block performed using 20 mL of Bupivacaine (0.25%) injected into the interspace between the popliteal artery and capsule of the knee. Patients will be blinded to their group allocation.
Reference Therapy	Reference is isolated adductor canal block
Key Procedures	Adductor canal block 15 mL 0.25% Bupivacaine, IPACK block with 20 mL 0.25% bupivacaine

CONFIDENTIAL

This material is the property of the NYU School of Medicine and Langone Medical Center. Do not disclose or use except as authorized in writing by the study sponsor

Statistical Analysis	Continuous and categorical baseline characteristics will be compared using Hedges standardized difference. Normally distributed data will be compared using t tests while non-normally distributed continuous outcomes will be assessed using the Mann-Whitney U test.
----------------------	--

CONFIDENTIAL

This material is the property of the NYU School of Medicine and Langone Medical Center. Do not disclose or use except as authorized in writing by the study sponsor

1 Background and Specific Aims

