1.2 Statistical Hypothesis

We hypothesize that patients who receive an IPACK block plus an ACB will have lower postoperative opioid consumption over the first 24 hours (measured in morphine equivalents) compared to those who an isolated ACB following anterior cruciate ligament reconstruction. Furthermore, the study group will report lower postoperative pain scores on POD1 than the control group. Failing to reject the null would signify that the IPACK block has no clinically relevant difference on post-operative opioid consumption outcomes following ACLR with BPTB autograft.

CONFIDENTIAL

This material is the property of the NYU School of Medicine and Langone Medical Center. Do not disclose or use except as authorized in writing by the study sponsor

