1.3 Objectives and Purpose

The goal of this study is to determine if the addition of IPACK block to the standard of care adductor canal block is superior to an isolated adductor canal block in decreasing postoperative pain, decreasing opioid consumption, and leads to increased duration of analgesia in patients undergoing ACLR. The primary objective will be to compare opioid utilization between the two arms within the first 72 hours after surgery, including intraoperatively, as measured by morphine equivalents. Our secondary objectives are measuring patient reported pain scores in PACU at 24 hours, 48 hours, and 72 hours, and at the first postoperative visit (POD 7).

2 Study Design and Endpoints

Arm 1: Experimental	Arm 2: Control
Sample Size: 50	Sample Size: 50
Medication: 15 mL of 0.25% Bupivacaine block of the saphenous nerve injected under ultrasound guidance via adductor canal and IPACK block with 20 mL of 0.25% Bupivacaine injected into the Interspace between the Popliteal Artery and Capsule of the Knee	Medication: 15 mL of 0.25% Bupivacaine block of the saphenous nerve injected under ultrasound guidance via adductor canal

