3.4 Recruitment and Consent

Surgeon will identify potential subjects during their initial preoperative visit at which the surgeon will discuss the study with the patient. Should the potential subjects agree, the surgeon will provide the researcher with the name and medical record number of the patient. Researchers will receive the name and MRN of potential subjects identified by treating physician (study team members not volunteers) will utilize EPIC to extract patient demographic and surgical information to determine study eligibility. Once eligibility is confirmed, the treating physicians (TPs) will be notified via email, and they will discuss the study with the patient in the clinic at least 1 day prior to surgery to allow potential subjects to review and consider participation in the study.

If a subject requests information regarding opting out of further recruitment for all research, subjects will be directed to contact study coordinator or have subjects contact [contact] or [name].

CONFIDENTIAL

This material is the property of the NYU School of Medicine and Langone Medical Center. Do not disclose or use except as authorized in writing by the study sponsor

Written consent will then be obtained on the day of surgery in the preoperative holding area by an authorized research team member or the treating physician (surgeon or anesthesiologist). Once the patient is enrolled, they will be assigned a subject ID number and be randomized into a treatment group.

Once enrolled in the study, subject medical records will be accessed once more after surgery (for the second and final time) using subject MRNs by authorized study team members to collect demographic data including age, BMI, sex, smoking history, past surgical history, intraoperative findings, and opioid consumption (mgs) in the PACU. Once collected, deidentified data will be stored in the MCIT-managed HIPAA-compliant and encrypted version of Redcap in addition to the MCIT governed, firewall protected shared drive located on the NYU MCIT network.

Data linking protected health information to the deidentified patient record number will be kept in a local password-protected computer. Only the principal investigator will have access to the identified data.

Process of Consent

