6.2 Analysis of Endpoints

Primary Endpoints:

1. Opioid utilization for the first 24 hours after surgery, including during surgery, calculated as oral morphine equivalent.

CONFIDENTIAL

This material is the property of the NYU School of Medicine and Langone Medical Center. Do not disclose or use except as authorized in writing by the study sponsor

Secondary Endpoints:

1. Patient reported VAS scores in PACU
2. Length of stay in PACU
3. Patient reported VAS scores on POD 1, POD 2, POD 3, POD7
4. Reaction to IPACK block
5. Mid-term functional outcomes will be assessed at 6 months: VAS, KOOS-PS, KUJALA, Tegner Activity Scale, strength, ROM.

Normally distributed data such as the primary outcome variable will be compared using the two-sample t-test. In the case that the data are not normally distributed, the Wilcoxon rank-sum test will be used instead. Categorical variable will be compared using the Chi-Squares unless other tests such as the Fisher's exact test are more appropriate.

All endpoints will be evaluated as fits the data set with graphical figures such as scatter plots, box-and-whisker plots, and frequency histograms to visualize the distribution of these outcomes and their relationships to covariates and treatment assignment. When appropriate descriptive graphical and tabular methods will also be estimated and presented in a graphical figure.

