6.4 Enrollment/Randomization/Masking Procedures

We will utilize randomization.com to generate a block randomization assignments for all 100 participants. Someone that is not a stakeholder in the study will make randomization envelopes, which include the study ID number, the treatment assignment, and dosage specifics. These randomization envelopes will then be distributed to the anesthesiologist pre-operatively by the authorized researcher after informed consent is obtained.

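### The hypothesis concerns postoperative opioid use, but the primary endpoint also counts intraoperative opioids, and section 6.2 omits the postoperative-only endpoint listed in the Summary

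*Combined protocol and SAP*

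**What the plan says.** The hypothesis in 1.2 is "lower postoperative opioid consumption over the first 24 hours" in the combined-block arm. The same section says that failing to reject the null would mean no clinically relevant difference in postoperative opioid consumption.

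The primary endpoint counts more than that, since it is a total "including during surgery":

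- Section 6.2: "Opioid utilization for the first 24 hours after surgery, including during surgery, calculated as oral morphine equivalent".
- Protocol Summary: "Opioid utilization for the first 72 hours after surgery, including during surgery, calculated as morphine equivalent".
- Section 1.3 (primary objective): "within the first 72 hours after surgery, including intraoperatively, as measured by morphine equivalents".

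Section 6.1, in its missing-data paragraph, describes the primary outcome as opioid use in the 24 hours after surgery and does not mention the intraoperative part.

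The Summary's secondary endpoints include "Opioid consumption Post-operatively". None of the five secondary endpoints in 6.2 concerns opioids.

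On masking, the Summary calls the trial single-blind, and 2.1 describes only patients as blinded. In 6.4 the envelopes, which carry the treatment assignment, are "distributed to the anesthesiologist pre-operatively". The only analgesic regimen described (2.1) is postoperative.

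On data capture, the record-extraction list in 3.4 ends with "intraoperative findings, and opioid consumption (mgs) in the PACU". The day-of-surgery schedule in 4.2.2 has a general opioid-usage item after the surgery step, and a separate item for opioid monitoring in the PACU.

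**The concern.** A test of the total does not test the hypothesis as written. The total mixes opioids taken after surgery with opioids given during it. With no masking or standard regimen described for the second part, a difference in the total could come from less pain after surgery, from a real reduction in intraoperative need, or from dosing by someone who knew the allocation. A null result could equally be a real postoperative effect hidden by variable intraoperative dosing, yet 1.2 would read it as a finding about postoperative use. The analysis that would tell these apart is in the Summary but missing from the section that governs the analysis.

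**Working it through.** **Can the intraoperative part be material?** From the conversion table in 15.1:

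- 0.1 mg IV fentanyl × 150 = 15 mg OME.
- Two 5 mg oxycodone tablets: 2 × 5 × 1.5 = 15 mg OME.

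So 0.1 mg of IV fentanyl counts as much as two tablets of the postoperative drug. The documents give no expected intraoperative doses.

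**The plan's own figure.** Section 6.3 states 42 per group, two-sided t test, alpha 0.05, power 0.80 and a moderate effect, without a number. At d = 0.5 (the conventional medium value, assumed) the t-test calculation gives 64 per group, not 42. Solving backwards, 42 per group needs d = 0.62. Both values are carried forward. At 50 per arm, power is 70% for d = 0.5 and 87% for d = 0.62.

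**Effect of adding the intraoperative part.** The documents give no SDs or correlations, so these inputs are assumptions:

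- d = postoperative effect, in postoperative SDs
- r = SD of intraoperative OME divided by SD of postoperative OME, taken as 0.5 to 1.0
- e = block effect on intraoperative OME, in intraoperative SDs
- zero correlation between the two parts

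Standardised effect on the total = (d + e × r) / √(1 + r²).

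Power at 50 per arm, two-sided 0.05:

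| d | e | r | Effect on total | Power |
|---|---|---|---|---|
| 0.5 | 0 | 0.5 | 0.5/1.118 = 0.45 | 60% |
| 0.5 | 0 | 1.0 | 0.5/1.414 = 0.35 | 42% |
| 0.62 | 0 | 0.5 | 0.62/1.118 = 0.55 | 78% |
| 0.62 | 0 | 1.0 | 0.62/1.414 = 0.44 | 58% |
| 0.5 | 0.25 | 0.5 | 0.625/1.118 = 0.56 | 79% |
| 0.5 | 0.25 | 1.0 | 0.75/1.414 = 0.53 | 75% |

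For d = 0.5 the loss vanishes when e = 0.5 × (√(1 + r²) − 1)/r:

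- r = 0.5: 0.5 × 0.118/0.5 = 0.12 SD
- r = 1.0: 0.5 × 0.414/1.0 = 0.21 SD

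A small true effect on intraoperative use is therefore enough to reverse the sign.

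Correlation also matters. With d = 0.5, e = 0 and a correlation of 0.3, the divisor becomes √(1 + r² + 2 × 0.3 × r), and power is 51% at r = 0.5 and 34% at r = 1.0.

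**Performance bias, if it occurred.** Suppose no true effect, and dosing that follows the allocation shifts the total by 0.1, 0.2 or 0.3 SD. At 50 per arm the nominal 5% test then rejects 8%, 17% or 32% of the time. The shifts are hypothetical; nothing in the documents indicates their size.

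**The case against.** Counting intraoperative opioids is deliberate: the Summary, 1.3 and 6.2 all state it. If the block is placed before surgery, which the envelope procedure suggests although the Summary describes administration during surgery, intraoperative need is a legitimate part of the treatment effect and including it may raise power. This stands, and it is why the total can remain primary.

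A reader might infer that the anesthesiologist who opened the envelope also chose the intraoperative doses, so that the primary endpoint is biased. The documents do not support that. Section 6.4 says who receives the envelopes, 2.1 does not say who opens them, and no section says who gives intraoperative opioids. What can be said is that no masking of that person is described.

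A reader might also infer that intraoperative doses will go uncollected, or that the two parts cannot be separated. Section 4.2.2 records opioid usage on the day of surgery, 4.3 records concomitant medications, and PACU and home use are collected in their own right, so postoperative use can be computed. The gap is that 3.4 names only PACU opioids, and 6.2 does not commit to the separate analysis.

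Finally, postoperative-only OME is not purely patient-driven: under 2.1, clinical staff decide the pain medication, and they are not described as masked either. This also stands. It limits what the fix achieves but does not remove the mismatch with 1.2.

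**Conclusion.** The mismatch is real. The plan hypothesises, and would interpret a null result as, a statement about postoperative opioid use, while its primary test is on a total that includes intraoperative use; the postoperative-only endpoint in the Summary is absent from 6.2. It should be corrected.

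Its size cannot be fixed from the documents. Under the stated assumptions, the total costs between 10 and 28 points of power at d = 0.5 (70% to 60%-42%), or 9 to 29 points at d = 0.62 (87% to 78%-58%), if the block leaves intraoperative use unchanged. It gains 5 to 9 points (70% to 75%-79%) at d = 0.5 if the block lowers intraoperative use by 0.25 SD. It would go too far to say that the plan loses power, or that the endpoint is biased. The supportable conclusion is that the total alone cannot show which of these happened.

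**What to change.** - Keep the stated total as primary if preferred.
- Restore postoperative-only OME to 6.2 as the first secondary endpoint, tested by the same method over the primary window. That window must first be reconciled: the Summary and 1.3 give 72 hours; 1.2, 6.1 and 6.2 give 24.
- Report intraoperative OME separately by arm.
- State in 1.2 that any conclusion about postoperative consumption, including from a null result, rests on the postoperative-only analysis.
- Align the extraction list in 3.4 with the day-of-surgery opioid item in 4.2.2 so that intraoperative opioids are named.

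The cost is wording and one additional analysis, with no change to the sample size or to care. The downside is that postoperative-only OME still contains PACU doses chosen by staff who are not described as masked, so the report should say so.

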2.1 Description of Study Design

RECRUITMENT PHASE/CONSENTING PHASE:

Surgeons will identify eligible patients via Epic during their initial clinic visit and discuss the study. Surgeons will provide research coordinator with the name and medical record number of eligible patients. If the patient meets the inclusion criteria outlined below and is agreeable, subjects will be first introduced to the study during one of their presurgical clinic visits and then consented on the day of surgery by a member of the research team. Patients will be made acquainted with the study prior to surgery. On DOS when they arrive 1.5/2 hours before surgery, we (study team members) will consent them in a private room and provide ample time to discuss and review any questions or concerns they may have.

BASELINE ASSESSMENTS:

Subjects will complete a baseline VAS McGill Pain scale, Kujala, KOOS-PS and Tegner Activity Scale

RANDOMIZATION PHASE:

Subjects scheduled to undergo ACLR with BPTB autograft will be randomized to either ACB with IPACK block or to ACB only. A randomization scheme will be created prior to start of study enrollment using the randomizer.org website to generate the assignment. Block randomization is commonly used in clinical trial design to reduce bias and achieve balance in the allocation of participants to treatment arms throughout the course of the study. Randomized block design allows us to account for variables so that observed differences are largely due to true differences between treatments and not to the variable. We will create blocks of four patients and in each block, two patients will be assigned to the IPACK + ACB group, and two to the ACB only

CONFIDENTIAL

This material is the property of the NYU School of Medicine and Langone Medical Center. Do not disclose or use except as authorized in writing by the study sponsor

group. Thus, patients in both groups will be evenly spread from the beginning to the end of the study.

A research coordinator will place the randomization results in sealed envelopes prior to recruitment. Each subject enrolled in the study will be assigned a number and the sealed envelope assigning the subject to the IPACK + ACB or ACB only will be opened on the day of surgery after the patient has signed consent agreeing to participate in the study.

Patients will be blinded to their group allocation. During peripheral block patients are sedated and postoperatively, the areas of infiltration will be covered by bandage.

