4.2.2 Enrollment/Baseline

Enrollment/Day of surgery (Visit 1, Day 0)

- Obtain informed consent of potential participant verified by signature on study informed consent form.
- Verify inclusion/exclusion criteria.
- Complete baseline global health and pain assessment
- Randomize to ACB or ACB + IPACK group
- Perform surgery with analgesic intervention determined by randomization
- Record vital signs, opioid usage, results of examinations, other pain assessments.
- Continue observation in PACU preceding discharge, including administration of VAS scores, pain questionnaire, and opioid usage monitoring.

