6.1 General Approach

The primary analysis will follow the intention-to-treat (ITT) principle in order to evaluate the true outcome of the intervention as experienced by the patient who is blinded to the intervention.

Continuous and categorical baseline characteristics will be compared using Hedges standardized difference. Normally distributed data will be compared using t tests while non-normally distributed continuous outcomes will be assessed using the Mann-Whitney U test.

It is anticipated that the data for some subjects will be incomplete for various reasons: missing diary entries, refusal to answer a question on the questionnaire, onset of illness, loss-to-follow-up, etc. All occurrences of incomplete data will be investigated to carefully document the reasons for the missing data. If the primary outcome (amount of opioid utilization for the first 24 hours after surgery) cannot be ascertained with a reasonable degree of certainty, the patient will be excluded from the study.

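### Baseline VAS is collected before randomisation but not used in the post-operative VAS comparisons; adjusting for it is a nearly free, probably modest gain in precision

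*Combined protocol and SAP*

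**What the plan says.** Section 2.1, under baseline assessments, states: "Subjects will complete a baseline VAS McGill Pain scale, Kujala, KOOS-PS and Tegner Activity Scale". The day-of-surgery schedule in section 4.2.2 includes "Complete baseline global health and pain assessment", listed ahead of the randomisation step. Section 4.1.1 also mentions a baseline pain assessment.

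The VAS outcomes in section 6.2 are PACU scores and "Patient reported VAS scores on POD 1, POD 2, POD 3, POD7". A further item lists VAS, KOOS-PS, Kujala and Tegner at 6 months.

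For the comparisons, section 6.1 says "Normally distributed data will be compared using t tests while non-normally distributed continuous outcomes will be assessed using the Mann-Whitney U test". Section 6.2 repeats the rule for endpoints: "In the case that the data are not normally distributed, the Wilcoxon rank-sum test will be used instead".

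Baseline data have one stated analytic use: "Continuous and categorical baseline characteristics will be compared using Hedges standardized difference" (section 6.1). Covariates enter the endpoint section only through plots, which are meant to "visualize the distribution of these outcomes and their relationships to covariates and treatment assignment". No ANCOVA, regression, mixed model or change from baseline is specified.

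Section 1.2 gives pain a place in the hypothesis: "the study group will report lower postoperative pain scores on POD1 than the control group".

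**The concern.** Baseline and outcome are measured on the same scale in the same patient, and the baseline value precedes allocation. If baseline pain predicts post-operative pain, part of the spread in post-operative VAS is explainable. An unadjusted test leaves that part in the error term, so the interval is wider and power lower than the collected data allow.

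The stake is the precision of the secondary pain comparisons. POD 1 deserves attention because section 1.2 hypothesises lower pain on that day. Enrolment is fixed at 100 (section 3.6), so using data already in hand is the cheap way to gain precision.

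There is also a prespecification benefit. The plan will quantify baseline differences and plot outcomes against covariates, but it does not say what follows if baseline pain looks unbalanced. Fixing the model in advance removes the choice.

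**Working it through.** **Inputs from the documents.** Two-sided alpha 0.05 and a two-sample t test; 42 per group stated as giving power 0.80 for an effect described only as moderate; 50 per arm enrolled (all section 6.3). Allocation is 1:1 in blocks of four, with no stratification by baseline pain (section 2.1).

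**Assumed, because the documents do not give them.** The standardised VAS difference d, and the correlation r between baseline and post-operative VAS.

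**The plan's own figure.** Section 6.3 puts no number on the effect, so 42 cannot be reproduced from its inputs. Solving backwards with the noncentral t, 42 per group at power 0.80 corresponds to d = 0.619. At d = 0.5 the requirement would be 64 per group. That mismatch is a separate matter; here it only suggests showing both d = 0.5 and d = 0.62. Neither value is stated for VAS.

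**Unadjusted test.** With n per arm, N = 2n and SD = 1, the noncentrality is d·√(n/2) on N − 2 degrees of freedom. For d = 0.5 and n = 50 this is 0.5 × 5 = 2.5 on 98 df, critical value 1.9845, power 0.697. The 95% CI half-width is 1.9845 × √(2/50) = 0.397 SD.

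**ANCOVA.** Residual variance becomes 1 − r². Chance baseline imbalance inflates the variance of the treatment contrast by (N − 3)/(N − 4) = 97/96 = 1.0104. The noncentrality is d·√(n/2) / √[(1 − r²)(N − 3)/(N − 4)] on N − 3 df. For r = 0.3: 2.5 / √(0.91 × 1.0104) = 2.607 on 97 df, power 0.733. The CI ratio is √(0.91 × 1.0104) × 1.9847/1.9845 = 0.959.

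| r | Power, d = 0.5 | Power, d = 0.62 | CI width relative to unadjusted |
|---|---|---|---|
| unadjusted | 0.697 | 0.866 | 1 |
| 0 | 0.692 | 0.863 | 1.005 |
| 0.1 | 0.697 | 0.866 | 1.000 |
| 0.2 | 0.710 | 0.876 | 0.985 |
| 0.3 | 0.733 | 0.893 | 0.959 |
| 0.5 | 0.812 | 0.941 | 0.871 |

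Break-even is at about r = 0.10.

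**With 10% of scores missing** (an assumed 45 per arm, d = 0.5, same formula): 0.650 unadjusted against 0.649, 0.663, 0.686 and 0.768 at r = 0.1, 0.2, 0.3 and 0.5.

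**Skewed scores.** Simulation with 20,000 trials per cell, 50 per arm, outcome exp(0.6 × a latent normal score) as an assumed stand-in for skewed VAS, latent d = 0.5:

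| Latent r | t test | Raw ANCOVA | Rank-sum | Rank ANCOVA |
|---|---|---|---|---|
| 0.2 | 0.627 | 0.634 | 0.673 | 0.689 |
| 0.3 | 0.626 | 0.652 | 0.671 | 0.704 |
| 0.5 | 0.621 | 0.718 | 0.674 | 0.780 |

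Raw-score ANCOVA is weaker than the planned rank-sum test at r = 0.2 and 0.3; ANCOVA on ranks is not.

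**Error rate.** Simulated type I error was 0.046 to 0.053 for all four methods, in normal and skewed cases alike. Not adjusting does not inflate it.

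**The case against.** The strongest reply is that this is a preference. Unadjusted comparison of a secondary outcome in a 1:1 randomised trial is acceptable, no statement in the plan is contradicted, and the primary endpoint is untouched. The whole benefit rests on r. Baseline VAS measures pain before surgery, while the early post-operative scores measure pain after new surgical trauma, modified by a block and variable opioid use, so r may well be low. At d = 0.62 the gain is under 3 points of power unless r is near 0.5, and nothing in the documents supports 0.5.

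Most of that stands and limits the size of the point. It does not remove it: the change is specific, the data are already collected, and the worst case is a loss of about 0.005 in power (0.697 to 0.692 at r = 0).

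Two smaller objections also stand. Raw-score ANCOVA can lose to the rank-sum test when scores are skewed. ANCOVA on ranks yields a difference in ranks, which is not readable in VAS units. The fix addresses both.

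A reader might infer that precision would improve most at POD 1. The documents do not support that. POD 1 is singled out only because section 1.2 hypothesises lower pain on that day; nothing shows that baseline predicts it better than the other days.

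**Conclusion.** A minor, nearly free improvement. The planned VAS tests ignore a baseline score that the schedule lists before randomisation. Adjusting for it gains nothing near r = 0.1, little at 0.2, a modest amount at 0.3 and a material amount only at 0.5. These sizes rest on assumed d and r, 50 per arm with complete data, and a linear relation with baseline.

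Two stronger readings should be avoided. A reader might infer that the unadjusted tests are biased; under randomisation they are not, and the simulated error rates agree. A reader might equally take this as an assurance that the VAS analysis is sound in every respect. It covers only the lack of adjustment. It does not address multiplicity across time points, the data-driven choice between t and rank-sum tests, or the exclusion in section 6.1 of patients whose primary outcome cannot be ascertained.

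**What to change.** In section 6.2, before unblinding, prespecify:

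- Post-operative VAS at each time point (PACU, POD 1, 2, 3 and 7) is compared by ANCOVA with arm and baseline VAS, reporting the adjusted difference and 95% CI in VAS units. The outcome is the post-operative score. An unadjusted change score has variance factor 2(1 − r), which is 1.4 at r = 0.3, and so would lose precision.
- Where the plan would use the rank-sum test, the p-value comes from the same model fitted to the ranks of baseline and post-operative VAS. The raw-scale adjusted difference and CI remain the reported estimate.
- A rule for a missing baseline VAS.
- The planned unadjusted tests are kept as sensitivity analyses.

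The same adjustment can be applied to the 6-month VAS, KOOS-PS, Kujala and Tegner scores, whose baselines are also listed in section 2.1. The primary opioid test does not change.

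The cost is SAP wording and slightly more programming, with no change to data collection, recruitment or care. The downside is a prespecified linearity assumption (in the baseline score or its rank) and a negligible loss of power if r is below about 0.10.
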